5.2 Independent Ethics Committee

IEC

According to applicable regulations, the appointed CRO or the Site Study Responsible will notify or obtain approval from the relevant IEC of the protocol, any amendments and the Subject Information Sheet / Informed Consent Form and other study-related documents, eg, Patient Report Outcome tools.

The appointed CRO or the Site Study Responsible will submit required documents to the IEC, such as:

- periodic updates on the progress of the study;
- notification of the end-of-study;
- a summary of the study results.

Global Research will keep an updated list of all submission and approval dates of all documents submitted to the IEC and will provide the Site Responsible with a copy of this list. Copies of the documents will be distributed upon request.

Authorities

Global Research or the appointed Contract Research Organization (CRO) will send required documents to the competent authority (CA) and/or other national or regional authorities.

Global Research will keep an updated list of submission and approval dates and a copy of all documents submitted.

5.3 Subject Information and Written Informed Consent

The Site Study Responsible must give the subject (and if applicable, parent or legal guardian) oral and written information about the study in a form that the subject can understand, and obtain the subject's written consent before collection of identifiable subject information (hereinafter referred to as personal data). Before consenting, the subject must be left with ample time to consider and to pose questions. Since the study is observational, the consent only concerns the data collection per se and is not consent to any interventional procedure or treatment.

The subject must agree that sponsor personnel, their representatives or IEC or CA personnel (national or other) may require direct access to the subject's data / personal records which were collected, processed and stored in an anonymous form.

The subject must agree that his / her data will be processed and stored in an anonymous form for evaluation of this study and any later overviews. Data may also be transferred in

anonymous form to third parties, e.g., other companies or authorities, that may be located in other countries with potentially different regulations for data.

The subject has the right to withdraw his/her consent at any time without prejudice. In the Informed Consent Form it is stated that if consent is withdrawn, any data collected before withdrawal of consent will be kept. The original, signed Informed Consent Forms must be kept on the Site.

For details, see the Subject Information Sheet and Informed Consent Form.

6 Study Design and Plan

This study is a 'non-interventional study' as defined in: G-STND-PV-006, G-SOP-MA-005, Directive 2001/20/EC (22) and will follow the guidelines for GPP (21).

This means that:

- The assignment of a subject to a particular therapeutic strategy is not decided in advance by the study protocol but falls within current practice.
- No additional diagnostic or monitoring procedures shall be applied to the subjects.
- Epidemiological methods shall be used for the analysis of collected data.

This is a multicentre, non-interventional study to determine the rate of control of disease activity. (Figure 1).

[figure not shown]

Figure 1. Study design scheme

During study appointment (Day1) data regarding disease activity, treatment patterns, burden of disease and quality of life will be collected (Figure 1). For patients with active disease at Day 1, a 12-month prospective evaluation will be conducted that will allow to follow the course of the disease.

At each site, eligible subjects will be identified consecutively as they attend scheduled clinical appointment (Day 1). Upon written consent, data regarding disease activity, treatment patterns, burden of disease and quality of life will be collected from medical records and PRO tools, including quality of life (SF-36, EQ-5D and IBDQ) and work productivity (WPAI) questionnaires. Retrospective data will refer to the previous three years and will include the previous IBD treatments (drug, dose, treatment duration, drug changes, surgeries), and use of other health resources related with the management of IBD.

UC patients with no or mild disease activity at Day 1 will not continue to 12-month follow up. CD patients with no or mild disease activity at Day 1 but with colonoscopy or calprotectin levels in the previous year suggestive of inadequate control of activity will progress to 12-month follow up.

6.1 Study Schedule

Planned Start of Study:	April 2016
Planned collection of first data point:	October 2016
Planned End of Study:	April 2018
Planned completion of the Study Report:	August 2018

This study will have duration of 6 months for the cross-sectional phase, with an additional follow-up of 12 months for the patients included in the prospective phase.

The Start of Study is defined as date of last protocol signature and planned to occur on April 2016. The collection of first data point (*first patient in*) will start during October 2016. The recruitment period is expected to last up to 6 months. The End-of-Study is defined as the date when the last subject completed follow-up period.

Takeda Brasil will ensure that End-of-Study notification is submitted to the concerned authorities and IEC for each site, for the country and for the complete study, as locally required.

Global Research will ensure that results are posted on “clinicaltrials.gov” and as required by local authorities.

Based on upcoming knowledge, Takeda might choose to terminate the study prematurely. In such case, the Committee(s), study sites, IECs and authorities will be informed promptly.

6.2 Discussion of Study Design

This is a non-interventional study designed to evaluate disease control, treatment patterns, burden of disease and health related quality of life among patients with IBD. The cross-sectional design with no control group is suitable and feasible to address the study objectives, which are mainly descriptive. Furthermore, the inclusion of a prospective follow-up for patients with active disease will enable an insight on how active CD or UC are managed in Brazil and what are the factors associated to achieving disease control.

In terms of external validity, two major points should be considered. First, the 20 study sites will be selected among reference public and private institutions for IBD management. It is expected that their patients will be representative of patients with moderate to severe IBD in Brazil. In addition, the inclusion and exclusion criteria are not restrictive and will enable the assessment of real-world data about IBD control in Brazil. Internal validity will be reinforced by training of Investigators and the use of same study procedures and forms. Hence, observation bias is not expected to occur during the cross-sectional and prospective evaluations. Although retrospective data collection is challenged by the quality of medical records, treatment patterns and hospitalizations are frequently recorded and no significant missing data is expected, which could lead to underestimation of health care utilization data. In addition, it is expected that completeness of medical records will be high in the last 3 years (retrospective period), namely regarding the use of biological treatments.

Because this is an observational study, some limitations should be minimized. All eligible patients will be consecutively invited to the study and the enrolment period will be of 6 months. Disease control may be underestimated due to selection bias, since patients with active IBD are expected to have more medical appointments and may be more easily invited. Nevertheless, the 6-month period will also enable the inclusion of patients with no or mild active disease.

Potential confounders will be addressed at:

- Enrolment – with the exclusion of patients with indeterminate or not classified colitis and that have participated in interventional clinical trials during the last 3 years. In fact, during a trial the subject has access to special and specific treatment and diagnosis procedures. The participation in an interventional trial during the previous 3 years may cause misunderstanding about treatment patterns and resources utilization, because in this project the retrospective data will be collected exactly about this period.
- Statistical analysis – with the inclusion in the logistic regression models of variables associated with both disease control and other variables of interest.

6.3 Selection of Study Population

Subjects should be included in the study only once.

Data erroneously collected from subjects for which written consent is not available, will not be included in or will be deleted from the database.

6.3.1 Inclusion Criteria

Subjects must meet all of the following inclusion criteria:

- 1) Male or female;
- 2) Subjects aged 18 years or older (at the time of diagnosis of moderate to severe UC or CD);
- 3) Diagnosis of moderate to severe CD or UC for at least 6 months prior to Day 1 appointment according the clinical or endoscopic criteria (23, 24, 25, 26, 27);
- 4) Subjects who provided the written informed consent.

In addition, for the prospective period, eligible patients should present at least one of the following criteria that will only be applied at Day 1:

- For CD patients:
 - HBI \geq 8 or
 - CDAI \geq 220 or

Considering that for CD patients, the disease activity may not be clearly documented only with clinical data, some objective criteria may be considered as entry criteria for the 12-month prospective period:

- colonoscopy in the previous year suggestive of inadequate control of activity
or
- calprotectin levels in the previous year suggestive of inadequate control of activity (i.e. calprotectin >200ug/g) (28).

For UC: partial Mayo Score ≥5

Note 1: UC patients with no or mild disease activity at Day 1 will not continue to follow up. CD patient with no or mild disease activity at Day 1 but with colonoscopy or calprotectin levels (i.e. calprotectin >200ug/g) in the previous year suggestive of inadequate control of activity will progress to 12-month follow up.

Patients that fulfill the above criteria (active disease) will be followed for 12 months, in order to explore patterns of care.

Note 2: Patients with colostomy and prospective period:

Although clinical scales defined above are impacted by colostomy these patients will not be excluded from the protocol to ensure the assessment of different clinical presentations of the IBD. In addition, patients with colostomy must follow the same criteria as above to be eligible to the prospective phase.

Note 3: Patients who are eligible for the prospective period, it means, with active disease at Day 1 but who during the 12 months period presents disease remission and/or no activity disease condition, must continue in the study.

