7.1 Data collection overview

Table 1. Study Flow Chart

Study variables	Day 1	Prospective period* (approx. 12 months)			
		Collection data points			
Timing of data collection	Day 1 visit	3-months (90 days \pm 14 days)	6-months (180 days \pm 14 days)	9-months (270 days \pm 14 days)	. End of fw-up (12 months) (365 days \pm 14 days)
Informed consent	X				
Inclusion criteria	X				
Exclusion criteria	X				
Anthropometric Information (Weight, Height, BMI)	X				
IBD type (CD or UC)	X				
Socio-demographic variables	X				
Smoking habits	X				
Family history of IBD	X				
Medical history / Comorbidities	X				
Date of diagnosis of CD or UC	X				
Date of diagnosis of moderate to severe CD or UC	X				
Clinical Characterization of Disease – (location, behavior, EIM)	X				
Steroid behavior	X				
Disease activity: CD (HBI score or CDAI); UC (partial/total Mayo Score)	X				X
Eligibility for 12-month follow up	X				
SF-36	X				
EQ-5D	X				
IBDQ**	X				
WPAI	X				
Previous treatments or regimens ^{1,2}	X				
Treatment started at Day 1	X				
Treatment at follow-up		X	X	X	X
Previous surgeries for IBD	X ²				
Hospitalizations	X ²				
Consumption of health resources related with IBD management	X ²				
Previous imaging and laboratory testing form	X ²				

¹ Excludes new treatments prescribed at Day 1 visit. ² Retrospective data collection (approx. 3 years)

* Prospective follow-up only for patients with active IBD at Day 1. In this period, data collection is expected to occur quarterly for all registered medical appointments.

** Not applicable for patients who have a colostomy or ileostomy.

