7.2 Study Variables

Data will be collected from medical charts and during the routine clinical appointment, for the following variables:

Socio-Demographic variables

- Date of birth;
- Gender;
- Professional status (employed, unemployed, retired, student, other).

Clinical variables

- IBD type: CD or UC;
- Date of diagnosis of CD or UC;
- Date of diagnosis of moderate to severe CD or UC (if not the same as previous);
- Family history of IBD;
- Smoking habits;
- Medical History / Comorbidities;
- Disease presentation [location, behavior, extraintestinal manifestations (EIM)];
- Steroid behavior (dependent or refractory);
- Colonoscopy in the previous year suggestive of inadequate control of activity (yes/no) (qualitative data/Mayo subscore);
- Calprotectin levels in the previous year suggestive of inadequate control of activity (i.e., calprotectin >200ug/g) (yes/no) (qualitative data);
- Eligibility for 12-month prospective follow up (yes/no).

Disease activity (at Day 1 and 12 months follow up appointment)

- For CD patients: Harvey Bradshaw Index (HBI) score or Crohn's Disease Activity Index (CDAI);
- For UC patients: 9-item partial Mayo Score (always collected) and the total Mayo score (when available).

The Harvey Bradshaw Index (HBI) score considers five easily assessed dimensions (general well-being, abdominal pain, number of liquid stools per day, abdominal mass, and complications). These dimensions are scored from the previous day (no diary cards are required). Patients with $HBI \geq 8$ are classified as presenting moderate to severe active disease (29).

The Crohn's Disease Activity Index (CDAI) evaluates the severity of signs and symptoms of CD. Collected data include information on the number of liquid stools, intensity of abdominal pain, general well-being, presence of comorbid conditions, use of medications for diarrhea, physical examination, and laboratory findings (abdominal mass, hematocrit, body weight), yielding 8 items that are combined with data from a 7-day diary to obtain the total CDAI score. Higher scores indicate a greater disease severity. Moderate to severe active CD is defined as $CDAI \geq 220$ (30).

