- Patients that had light or no activity of disease at the end of the 12-month follow-up will be compared with patients that remained with active disease, regarding socio-demographic, clinical and treatment variables of interest. Similarly to the cross-sectional analysis, the comparison of categorical variables will be conducted with Chi-square or Fisher exact tests and t-student or Mann-Whitney tests will be used to compare quantitative variables.
- If applicable, variables associated with having light or no activity 12 months after baseline will be identified through logistic regression models for each IBD disease and OR (95%CI) will be presented.

- In addition, survival analysis with Kaplan Meier curves and Cox regression models will be used (if applicable) to identify factors associated with achieving light or no activity with baseline treatment (continued or initiated at baseline), during follow-up. In this analysis, patients that remained with active disease or that change treatment due to lack of disease control will be censored and, conversely, success will be defined as having light or no active disease. Time to success will be considered as dependent variable in survival analysis methods.
- The number and reason for treatment changes during follow-up will be summarized and treatment patterns during prospective period will also be described. Patients with treatment changes will be compared with those without changes, regarding main socio-demographic, clinical and treatment baseline variables. The comparison of categorical variables will be conducted with Chi-square or Fisher exact tests and t-student or Mann-Whitney tests will be used to compare quantitative variables.
- If applicable, Poisson regression models based on generalized linear equations will be used to examine the relationship between variables of interest and the incidence of the treatment changes during follow-up.

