- 7) Longitudinal analysis: A sensitivity analysis will be performed to determine the proportion of patients with active IBD after 12 months, among patients who had moderately to severely active IBD at Day 1 (baseline), considering the CDAI/ HBI (for CD patient) or Mayo (for UC patients) scores collected during the IBD specialist appointments, allowing a time window of 1 month (30 days) to assess disease activity ( $M12 = (Day1 + 365 \text{ days})$  or  $(Day1 + 365 \text{ days}) - (30 - 1 \text{ days})$ ). The results will be presented as percentage and the 95% confidence interval will be calculated.

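### Crohn's patients who enter follow-up on colonoscopy or calprotectin alone already meet the month-12 success state at Day 1, and several month-12 control analyses do not explicitly exclude them

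*Protocol*

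**What the plan says.** Entry. Protocol 6.3.1 (repeated in SAP 4.1) sets the terms for the prospective period: "eligible patients should present at least one of the following criteria that will only be applied at Day 1". For CD these start with the HBI and CDAI cut-offs. The section then adds a second route: "Considering that for CD patients, the disease activity may not be clearly documented only with clinical data, some objective criteria may be considered". The objective criteria are "colonoscopy in the previous year suggestive of inadequate control of activity" or a calprotectin result above 200 ug/g in the same year. Note 1 spells out the consequence: a "CD patient with no or mild disease activity at Day 1 but with colonoscopy or calprotectin levels" suggestive of inadequate control goes on to follow-up. The section then labels all patients who meet any of these criteria as having active disease. Ulcerative colitis (UC) has no objective route.

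Measurement. The activity row of Table 1 in Protocol 7.1, "Disease activity: CD (HBI score or CDAI); UC (partial/total Mayo Score", is marked at Day 1 and at 12 months. Colonoscopy and calprotectin are not scheduled again. Protocol 7.2 records calprotectin as "Calprotectin levels in the previous year suggestive of inadequate control of activity (i.e., calprotectin >200ug/g) (yes/no) (qualitative data", and the imaging and laboratory form is a retrospective Day 1 item.

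Analysis. SAP 7.2 defines the longitudinal population as everyone in the prospective period, described as patients with active IBD. Protocol 10.3 gives the month-12 CD proportion among patients with HBI or CDAI at the active level at Day 1. SAP 7.6 keeps that wording (its formula is redacted), and so does the sensitivity analysis in SAP 8, item 7, "considering the CDAI/ HBI (for CD patient) or Mayo (for UC patients) scores collected during the IBD specialist appointments". The month-12 comparison in Protocol 10.3 is worded differently: "Patients that had light or no activity of disease at the end of the 12-month follow-up will be compared with patients" who remained active. The Kaplan-Meier/Cox analysis defines success as reaching light or no activity.

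**The concern.** The word active has two meanings in these documents. In the objectives and endpoints it means HBI or CDAI at or above the cut-off. In Protocol 6.3.1 and SAP 7.2 it covers everyone admitted to follow-up, including CD patients who were below the cut-off at Day 1.

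For that second group, the state counted as success at month 12 is the state they were in at Day 1. If nothing changes they count as controlled. In a comparison or logistic model of control they fall mostly among the successes, so a characteristic that goes with entry on objective evidence (for example, being tested in routine care) can appear as a factor associated with control. In the survival analysis they have no time at risk in the active state, so their time to success has no meaning.

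Assessing 12-month activity is a secondary objective, and Protocol 6.2 gives finding factors associated with control as a reason for the follow-up. These are the results exposed.

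**Working it through.** **1. The plan's own CD count.** Protocol 10.6 and SAP 6: 400 patients x 50% CD x 20-30% inadequate control = 40 to 60. This reproduces the stated 40-60. Nothing is added for patients entering by the objective route.

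**2. Two kinds of CD entrant, classified by the index.**

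| Entrant | Day 1 | Month 12 if unchanged |
|---|---|---|
| At or above the cut-off | active | active |
| Below the cut-off, objective evidence only | no or mild activity | no or mild activity, counted as controlled |

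**3. Which month-12 analyses state a Day 1 index restriction.**

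- Active CD proportion (Protocol 10.3): yes, in its caption and denominator.
- Sensitivity analysis (SAP 8, item 7): yes, in words.
- Proportion of controlled patients (Protocol 10.1.2, SAP 7.1): no denominator given.
- Proportion by region (SAP 8, item 5): longitudinal dataset, no restriction stated.
- Controlled versus still active, and logistic model (Protocol 10.3, SAP 7.6): none stated.
- Kaplan-Meier and Cox (Protocol 10.3, SAP 7.6): none stated.

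**4. Effect on the CD control proportion.** Let n be the number of index-active entrants, m the number of objective-only entrants, and c and q the shares below the cut-off at month 12 in each group.

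- Restricted to index-active patients: control = c. Objective-only entrants contribute 0 points.
- Pooled: control = (n x c + m x q) / (n + m). The difference from c is m / (n + m) x (q - c).

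Only n has a basis in the documents (40 or 60, taking the planned count as index-active). The values of m, c and q are assumptions: m = 10-40, c = 50%, q = 70-100%.

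- Low end, n = 60, m = 10, q = 70%: (30 + 7) / 70 = 52.9%, or +2.9 points.
- High end, n = 40, m = 40, q = 100%: (20 + 40) / 80 = 75.0%, or +25.0 points.

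Varying c, with n = 40 and q = 80%:

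- c = 40%: m = 10 gives (16 + 8) / 50 = 48% (+8); m = 40 gives (16 + 32) / 80 = 60% (+20).
- c = 60%: m = 10 gives (24 + 8) / 50 = 64% (+4); m = 40 gives (24 + 32) / 80 = 70% (+10).

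**5. Mismatched numerator and denominator.** The numerator in the Protocol 10.3 formula does not itself repeat the Day 1 condition; the caption supplies it. If objective-only entrants active at month 12 were counted in the numerator alone, control would be 1 - [n(1 - c) + m(1 - q)] / n. With n = m = 40, c = 50% and q = 70% this is 1 - (20 + 12) / 40 = 20%, or -30 points; with q = 100% the change is 0. The direction of any error therefore depends on how the two sets are programmed.

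**The case against.** The strongest defence is that the only month-12 CD proportion given a formula uses one yardstick throughout: HBI or CDAI at Day 1 in the denominator and HBI or CDAI at month 12 in the numerator. This stands. A reader might infer from the wider entry rule that 12-month CD control is overstated in general, or that some improvement is bound to appear. The documents do not support that. An index-active patient who does not change stays active, and objective-only entrants are outside that denominator. Objective evidence opens follow-up so that patterns of care can be explored; it does not define the activity endpoint.

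A second defence is that Protocol 10.3 introduces its longitudinal analyses as being for patients with active IBD at Day 1, and that the comparison speaks of patients who remained active. Read with the Section 3 definition, that would restrict everything. It is a possible reading, but not a safe one. Protocol 6.3.1 and SAP 7.2 apply the same label to all entrants, and the SAP table index assigns the month-12 prevalence and comparison tables (Tables 90 to 98) to the longitudinal population.

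Third, Protocol 6 bars additional diagnostic procedures, so the absence of repeat testing follows from the design and is not itself a fault. This also stands. Results from routine care could be recorded, but from a selectively tested subset.

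A reader might also infer that an old abnormal result counts at entry despite a later normal one, and ask for a new entry rule. Protocol 6.3.1 does not say how several results are handled. SAP 8 places even Amendment 1 at or after the end of recruitment, so changing entry would achieve nothing. The lack of an objective route in UC has little effect, because CD and UC are summarised and modelled separately.

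**Conclusion.** The point holds as a gap in the definition of the analysis population. For the captioned CD proportion in Protocol 10.3 the effect is 0 points. For the controlled proportion, the month-12 comparison, the logistic model and Kaplan-Meier/Cox, the documents do not say whether objective-only CD entrants are included, and the definition in SAP 7.2 includes them. If they are pooled, CD control is inflated whenever q exceeds c, which is likely because they start below the cut-off. The effect disappears if q equals c. The range of +2.9 to +25.0 points rests on assumed m, c and q and is an illustration, not an estimate. For the regression and survival models the problem is one of meaning as much as size: part of the sample has no active state to leave.

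**What to change.** In SAP 7.2 and 7.6, and in Protocol 10.3, state that every month-12 CD control analysis is limited to patients at or above the HBI/CDAI cut-off at Day 1, in numerator and denominator alike. This covers the controlled proportion, the regional comparison in SAP 8 item 5, the controlled-versus-active comparison, the logistic model and Kaplan-Meier/Cox. Report objective-only CD entrants as a separate descriptive stratum, with their number and month-12 scores, and reserve the word active for the index definition. Because the cut-off will be restated, reconcile CDAI at or above 220 (endpoints) with CDAI above 220 (formulas).

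Optionally, abstract the date and result of any routine-care colonoscopy or calprotectin during follow-up, as descriptive data only, and state how many patients were tested.

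The main change needs wording only: Day 1 scores, the two objective items and follow-up eligibility are already collected. Its price is a smaller CD sample in models that are already small. The optional item adds eCRF fields at the quarterly data collection already planned.
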